2.2.2 Rationale for Doses and Dose Schedule to be Studied

Na-APR-1 (M74)/Alhydrogel[®] has not yet been administered to individuals living in a hookworm-endemic area, whereas *Na*-GST-1/Alhydrogel[®] (with or without GLA-AF) has been tested at the same field site as that proposed in the study described in this protocol, in healthy hookworm-exposed adults without any observed safety concerns. Therefore, in the study described in this protocol, *Na*-APR-1 (M74)/Alhydrogel[®] will be administered in escalating doses, whereas the dose of *Na*-GST-1/Alhydrogel will be the maximum tolerated dose in the previous studies of this vaccine candidate. Doses of 10, 30 and 100µg of *Na*-APR-1 (M74) were selected for evaluation

based on preclinical studies and to maintain an equal fold-increase in the amount of antigen. The 10µg dose was also selected as the lowest dose for clinical trials due to the difficulty in precisely dispensing lower volumes (both vaccine antigens have been formulated at a protein concentration of 100µg/ml). As mentioned above, selection of the 100µg dose of *Na*-GST-1 is based on preliminary safety and immunogenicity data from the ongoing Phase 1 study of 10, 30 and 100µg *Na*-GST-1 with or without 2.5µg GLA-AF administered to 102 healthy Brazilian adults (protocol SVI-10-01), and the ongoing Phase 1 study of 10, 30, and 100µg of *Na*-GST-1 with or without 1µg or 5µg GLA-AF administered to 40 healthy US adults (protocol SVI-11-01). To date, 100 µg *Na*-GST-1/Alhydrogel administered with 5 µg GLA-AF has been very well tolerated, with no observed vaccine-related Serious Adverse Events and only mild to moderate local injection site pain and tenderness being the most commonly reported adverse events. Unfortunately, the addition of GLA-AF (any dose) to *Na*-GST-1/Alhydrogel did not significantly increase IgG levels to the *Na*-GST-1 antigen. Therefore, GLA-AF will not be tested further in combination with *Na*-GST-1/Alhydrogel.

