11.2 Sample Size Considerations

This Phase 1 trial is not powered to detect statistically significant differences between groups. Even though comparative statistics for the safety variables will be computed, the study will have low power to detect anything other than very large differences in the incidence of local injection site and systemic side effects between the vaccination groups. This is done weighing the need to detect any possible untoward reactions against the need to limit the number of volunteers involved for safety purposes. The sample size of 60 for this study is within the range commonly used in Phase 1 trials for the initial assessment of the safety, tolerance and immunogenicity of investigational vaccines.

The primary objective of the study is to estimate the frequency of vaccine-related adverse events. Therefore, rather than providing a statistical power calculation for a specific hypothesis, we illustrate below the probability of observing one or more events, such as an adverse event of a particular type, for a single vaccine dose (N=20), formulation (N=30), or for all participants (N=60) under different assumptions of the true rate at which such events occur in the population.

	Probability of Observing 1 or More Events		
	N=20	N=30	N=60
"True" (but unknown) Probability of an Event			
0.5%	9.54%	13.96%	25.97%
1.0%	18.21%	26.03%	45.28%
3.0%	45.62%	59.90%	83.92%
5.0%	64.15%	78.54%	95.39%
10.0%	87.84%	95.76%	99.82%

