As illustrated in the table above, the study will have high probability ($\geq 80\%$) of detecting events that are commonly occurring in the population. For example, with a sample of 20 participants (which is equivalent to the size of each dose group of *Na*-APR-1 (M74) in this study), there is an 87.84% probability of observing 1 or more events when the events occur at a rate of 10.0% in the population. As the sample size increases, the study is able to detect events that occur at lower rates. For example, using a sample size of 30 participants (which is equivalent to the number of participants assigned to vaccine co-administration in this study vs. *Na*-APR-1 (M74) alone), there is a 78.54% probability of observing 1 or more events that occur at a rate of 5% in the population. Using a sample of size 60 (equivalent to the entire study population) there is an 83.92% probability of observing 1 or more events that occur at a rate of 3% in the population. Detection of rare events—those that occur at a rate of 1% or less in the population—is not likely in this study.

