11.3 Planned Interim Analyses

11.3.1 Safety Review

Descriptive and hypothesis-testing approaches will be used to estimate AE rates and to compare these rates in the difference doses and formulations of *Na*-APR-1 (M74) alone or co-administered with *Na*-GST-1. Estimates will be presented with their 95% confidence intervals. Formal statistical tests, as outlined below, will be used to compare doses. No formal adjustments for multiple comparisons will be made. Statistical tests will use a two-sided significance level of 5%.

The proportion of subjects with at least one injection site AE will be compared by vaccine allocation (e.g., *Na*-APR-1 (M74) vs. *Na*-APR-1 (M74) co-administered with *Na*-GST-1), by *Na*-APR-1 (M74) dose, and by GLA-AF dose.

Laboratory results (hematological and clinical chemistry) will be examined for trends over time and any clinically significant values for individuals will be reported.

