11.4 Final Analysis Plan

The purpose of this trial is to estimate AE rates and patterns of immune response as well as to compare these rates and patterns between the investigational vaccines, when they are administered separately or when they are co-administered.

This section briefly describes the statistical methods to be used; a detailed analytical plan will fully describe the methods. The analytical plan will discuss the planned approaches to missing data. Deviations from the original analytical plan will be thoroughly documented and reported to the Sponsor.

Descriptive and hypothesis-testing approaches will be used to meet the protocol objectives as stated in **Section 3**. Estimates will be presented with their 95% confidence intervals. Formal statistical tests, as outlined below, will be used to compare doses. Statistical tests will use a two-sided significance level of 5%.

Note: For the analyses described below, historical safety data from a Phase 1 clinical trial conducted at the same study site and in the same subject population (study SVI-10-01, see **Section 2.1.6** above for a description of this trial) will be used to obtain a comparison of *Na*-GST-1/Alhydrogel. As well, stored serum and cell specimens from those study participants will be used in the immunological assays to obtain data on subjects administered *Na*-GST-1/Alhydrogel without co-administered *Na*-APR-1 (M74). These specimens from SVI-10-01 will be assayed at the same time as those newly collected from the study described in this protocol.

Primary Objective: To evaluate the safety and reactogenicity of three different dose concentrations of Na-APR-1 (M74) adjuvanted with Alhydrogel® or Alhydrogel® plus GLA-AF and administered either with or without Na-GST-1, in healthy Brazilian adults.

AEs will be coded according to Medical Dictionary of Regulatory Activities (MedDRA™) preferred terms. The frequency, severity, and relationship of AEs per each vaccine formulation and dose cohort of Na-APR-1 (M74) and co-administration status with Na-GST-1 will be presented in tabular form using the MedDRA™ coded term and organized by MedDRA™ System, Organ, and Class (SOC) designations.

- The frequency of immediate, systemic, and local injection site AEs will be summarized by SOC and preferred term.

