- Line listings of clinical and laboratory AEs classified as immediate (within the first 60 minutes), systemic, and local will be displayed in tables stratified by dose cohort and formulation of Na-APR-1 (M74) and formulation (i.e., no GLA-AF or 5 µg GLA-AF).
- AEs will be summarized by severity and relationship to vaccine formulation by individuals and dose of Na-GST-1, Na-APR-1 (M74), and GLA-AF.
- The frequency of vaccine-related SAEs will be tallied as well as summarized by body system, by vaccine formulation and dose cohort.

Primary Outcome Measures:

The following summary parameters will be evaluated for each dose and formulation of Na-APR-1 (M74) alone or co-administered with Na-GST-1:

1. Frequency of solicited injection site and systemic reactogenicity, graded by severity, on the day of each study vaccination through 14 days after each study vaccination.
2. Frequency of study vaccine-related serious adverse events from the time of the first study vaccination through approximately 9 months after the last study vaccination.
3. Frequency of clinical safety laboratory adverse events.
4. Frequency of unsolicited adverse events, graded by severity, from the time of each study vaccination through approximately 1 month after each study vaccination.
5. Frequency of new-onset chronic medical conditions through approximately 9 months after the third study vaccination.
6. Frequency of Adverse Events of Special Interest through approximately 9 months after the third study vaccination.

Analysis Plan:

The proportion of participants with at least one injection site AE will be compared by Na-APR-1 (M74) vaccine formulation and dose cohort and co-administration status with Na-GST-1. We will test the null hypotheses that the type and number of adverse events is the same across all groups by Fisher's exact test.

Laboratory results (hematological and clinical chemistry) will be examined for trends over time and any clinically significant values for individuals will be reported.

Secondary Objective: To assess the impact of co-administering Na-APR-1 (M74) and Na-GST-1 on antibody production by measuring the antibody levels to each antigen on study Day 126.

Secondary Outcome Measures:

The following parameters will be evaluated for each dose and formulation of Na-APR-1 (M74) alone or co-administered with Na-GST-1:

1. The IgG level by an indirect enzyme-linked immunosorbent assay (ELISA) on approximately Day 126.

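### Fisher's exact test is valid for the adverse event proportions, but in the pooled 30 vs 30 comparisons it gives up power that Boschloo's exact test keeps at the same 5% level

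*Protocol*

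**What the plan says.** Section 11.4 sets the level ("Statistical tests will use a two-sided significance level of 5" per cent). Under the primary objective it states the contrasts: "The proportion of participants with at least one injection site AE will be compared by Na-APR-1 (M74) vaccine formulation and dose cohort and co-administration status". It then names the test: "We will test the null hypotheses that the type and number of adverse events is the same across all groups by Fisher's exact test". No other test is named for AE proportions.

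Section 11.3.1 lists the same endpoint for the interim safety review: "The proportion of subjects with at least one injection site AE will be compared by vaccine allocation", by Na-APR-1 dose and by GLA-AF dose. It names no test of its own.

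The sizes come from Section 11.2, which describes a sample of 30 as one "which is equivalent to the number of participants assigned to vaccine co-administration in this study vs" Na-APR-1 alone, and gives 20 per dose. Section 11.2 also concedes low power for all but very large differences. Section 2.2.2 says the three doses were chosen "to maintain an equal fold-increase in the amount of antigen".

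**The concern.** Fisher's test conditions on the total number of events. With 30 per arm the attainable p-values are coarse, so the achieved error rate sits well below the 5% the plan allows. The unused error rate is lost power. Section 11.1 hypothesises that co-administration does not raise reactogenicity, so a test that falls short of significance more often than it needs to errs in the reassuring direction. Section 2.2.3 ties the interim report to the decision on trials in children. An alternative exact test with the same guarantee costs nothing. Separately, a test of equality across groups makes no use of the dose order.

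**Working it through.** **Inputs.** Level 0.05, two-sided (11.4). Arms of 30 vs 30: six Groups with 5 per arm, 6 × 5 = 30 (Section 4, 11.2). Dose cohorts of 20: two Groups of 10 (same places). AE rates for these comparisons are not in the protocol, so those below are assumptions. The nearest background figure is 7.6% to 16.7% local reactions for licensed aluminium-adsorbed vaccines (2.1.10).

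**1. The plan's own figures.** The table in 11.2 is 1 − (1 − p)^N. For example, 1 − 0.90^20 = 87.84%, 1 − 0.95^30 = 78.54% and 1 − 0.97^60 = 83.92%. All 15 cells reproduce. The protocol states no power or achieved size for Fisher's test.

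**2. Why Fisher's test falls short of 5%.** Take all events in one arm:
- 5/30 vs 0/30: p = 2 × C(30,5)/C(60,5) = 2 × 142,506/5,461,512 = 0.0522, not significant.
- 6/30 vs 0/30: p = 2 × C(30,6)/C(60,6) = 2 × 593,775/50,063,860 = 0.0237.

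The p-value jumps over 0.05, and this happens for most totals.

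**3. True size at 30 vs 30.** For a common rate π, sum Bin(a; 30, π) × Bin(b; 30, π) over those of the 31 × 31 = 961 tables with p ≤ 0.05. Boschloo's test takes Fisher's p as its statistic and rejects when it is at or below the largest cut-off that keeps the maximum size within 5%. Here that cut-off is 0.0692. Because 0.0692 > 0.05, its rejection region contains Fisher's; the 5 vs 0 table above is one it adds.

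| Common rate | Fisher size | Boschloo size |
|---|---|---|
| 7.6% | 0.52% | 1.68% |
| 10% | 0.94% | 2.33% |
| 16.7% | 1.92% | 3.00% |
| 30% | 2.61% | 3.65% |
| 50% | 2.74% | 4.67% |
| Maximum | 2.74% | 4.69% |

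**4. Power at 30 vs 30 (assumed rates).** The same sum with different rates in the two arms.

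| True rates | Fisher | Boschloo | Gain |
|---|---|---|---|
| 10% vs 30% | 37.2% | 42.5% | 5.3 |
| 30% vs 50% | 25.9% | 34.1% | 8.2 |
| 10% vs 40% | 70.5% | 74.3% | 3.8 |
| 20% vs 50% | 59.6% | 67.1% | 7.5 |
| 30% vs 60% | 56.1% | 64.7% | 8.6 |
| 10% vs 50% | 91.4% | 93.0% | 1.6 |
| 20% vs 60% | 85.1% | 89.9% | 4.8 |

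With lower rates from 5% upward in steps of 5 points, the gain is 3.8 to 9.2 points for differences of 20 to 30 points, and 1.2 to 4.9 points for a difference of 40 points.

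**5. Rates that differ by dose within an arm.** With 10 per dose in each arm, 20/40/60% against 40/60/80%: 24.4% (Fisher) and 31.8% (Boschloo). The gain remains.

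**6. Within a Group, 5 vs 5.** Fisher's test rejects only for 5 vs 0, 4 vs 0 and 5 vs 1, in either direction. At a 50% rate that is (2 + 10 + 10)/1,024 = 2.15%. The next tables in order (3 vs 0 and 5 vs 2) would add 40/1,024, giving 62/1,024 = 6.05%, above 5%. Boschloo's test therefore has the same rejection region and no gain.

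**7. Three doses, 20 each.** Fisher's test against an exact Cochran-Armitage trend test with equally spaced scores (log dose), all 21³ = 9,261 tables.

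| True rates | Fisher | Trend |
|---|---|---|
| 10/20/30% | 21.5% | 28.4% |
| 10/25/40% | 44.3% | 54.3% |
| 20/40/60% | 63.0% | 71.0% |
| 10/20/40% | 45.6% | 56.5% |
| 20/50/50% | 49.8% | 43.8% |
| 30/50/30% | 22.3% | 2.5% |

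For common rates of 10% to 50%, the size is 2.3% to 4.4% for Fisher's test and 2.4% to 3.8% for the trend test. The dose difference therefore comes from assuming a steady rise, not from a lower achieved level.

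**The case against.** The strongest reply is that there is no error to correct. A test whose true size is below 5% complies with a 5% level, and Fisher's test is standard for sparse AE tables. That stands: a reader might infer that the plan breaks its own significance level, and it does not.

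A reader might also infer that a real rise in reactions will be missed. The documents do not support that. Section 11.1 makes the analysis primarily descriptive, Section 11.4 asks for estimates with 95% confidence intervals, and escalation and halting rest on event counts and committee review (Sections 4, 9.5 and 9.6.2). No stated decision turns on p crossing 0.05.

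Section 11.4 also defers full methods to a detailed analytical plan. That weakens the point but does not remove it, because the protocol itself names the test.

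The 30 vs 30 Fisher comparison is an inference: the test sentence says "is the same across all groups by Fisher's exact test", while the two-group contrast comes from the sentence before it and from Sections 11.2 and 11.3.1. Pooling also ignores that co-administration was randomised within six Groups. If rates climb steeply with dose (10/40/80% in both arms), the pooled Boschloo size falls to about 1.5%, and a stratified exact test may do better. Fisher's pooled size is then lower still (0.6%), so the ranking of these two tests does not change.

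Finally, a reader might take the dose comparison to suffer from the same shortfall in level. It does not, and the trend test is a trade-off rather than a free gain. Dose was assigned by open sequential enrolment and not masked (Sections 4 and 5.3.2), so a smaller p-value would not separate dose from cohort or reporting effects. The same caution applies to the GLA-AF contrast.

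**Conclusion.** The point holds as a minor efficiency improvement. In the pooled 30 vs 30 comparisons Fisher's test uses at most 2.7% of the allowed 5%. Boschloo's test uses up to 4.7%, still controls the level, and cannot lose power against it. These statements about size and ordering need no assumed rates, only independent binomial counts with one common rate under the null hypothesis.

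The amount of power does depend on assumed rates: about 4 to 9 points for differences of 20 to 30 points, under 5 points for 40-point differences, none at 5 vs 5. For the very large differences that Section 11.2 has in mind, little changes. For the dose comparison, the trend test gains about 7 to 11 points in the steadily rising cases computed, loses about 6 points for a plateau, and misses a rise followed by a fall. That supports an addition, not a replacement.

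**What to change.** In Sections 11.3.1 and 11.4, name Boschloo's exact test, two-sided at 5%, for the pooled participant-level AE comparisons of two groups: co-administered vs alone, and GLA-AF 0 vs 5 µg. State explicitly that these are 30 vs 30 comparisons, and report the difference in proportions with the planned 95% confidence interval beside each p-value. Fisher's test can stay for the 5 vs 5 tables, where the two coincide.

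Optionally, keep Fisher's test for the three-dose comparison and add a two-sided exact Cochran-Armitage trend test on log dose as a supportive analysis. Label it as one more unadjusted test, and note that it is weak against plateau and non-monotone patterns and that dose was neither randomised nor masked.

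The cost is a few lines of analysis text and standard software. No subjects, visits or data are added.

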2.1.6 Clinical Experience with *Na*-GST-1/Alhydrogel® Hookworm Vaccine

The *Na*-GST-1/Alhydrogel® hookworm vaccine has been tested in two Phase 1 clinical trials in humans in both the United States (n=40) and Brazil (n=102). So far, no significant reactogenicity or safety issues have been observed in these two studies. In study SVI-11-01 in healthy, hookworm-naïve American adults conducted in Washington, DC, 40 volunteers received three vaccinations with up to 100 µg *Na*-GST-1/Alhydrogel® administered with or without up to 5 µg GLA-AF (NCT01385189). Mild to moderate injection site pain and tenderness were observed in a minority of study subjects; other common adverse events have included mild to moderate headache and nausea. Vaccinations were completed in this study in early January 2014; interim immunogenicity results are currently pending.

The trial in Brazil (SVI-10-01) has tested *Na*-GST-1/Alhydrogel® in both hookworm-unexposed (n=36) and hookworm-exposed (n=66) healthy adults (NCT01261130). This study was initiated

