in Belo Horizonte, a large urban area in the Brazilian state of Minas Gerais, in healthy, hookworm-unexposed adults (n=36) who received up to 100 µg *Na*-GST-1/Alhydrogel[®] with or without 2.5 µg GLA-AF. After no significant adverse events were observed in these volunteers, vaccinations were begun at the hookworm-endemic region of Americaninhas in Minas Gerais; this second part of the trial was a randomized, controlled, double-blind study in which subjects received up to 100 µg *Na*-GST-1/Alhydrogel[®] with or without 2.5 µg GLA-AF (n=60), or the recombinant hepatitis B vaccine (n=6). All volunteers in this study received three intramuscular injections at 0, 2, and 4 months and are being followed for 12 months after the final vaccination. Vaccinations were completed in August 2013 and preliminary immunogenicity results will be available mid 2014. In this study, the *Na*-GST-1/Alhydrogel[®] (with or without GLA-AF) appears to be safe and well tolerated in both hookworm-unexposed and hookworm-exposed adults. No vaccine-related SAEs have occurred and the vaccine appears to be well tolerated, with mild-to-moderate injection site pain and tenderness being the most common vaccine-related adverse events. Also, it is important to note that all volunteers who were screened for study SVI-10-01 were tested for IgE antibodies to *Na*-GST-1: none of these individuals in either Belo Horizonte or Americaninhas had detectable IgE antibodies to the vaccine antigen, as determined by ELISA.

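### Section 11.4 calls the historical Na-GST-1 comparator same-site and same-population, but 36 of its 102 participants were hookworm-unexposed urban adults, and no restriction is stated

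*Protocol*

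**What the plan says.** The note that opens the analyses in protocol Section 11.4 brings in SVI-10-01 as the source of data on Na-GST-1 given alone. It states that SVI-10-01 was "conducted at the same study site and in the same subject population" and refers to Section 2.1.6 for a description. Historical safety data are to be used, and "stored serum and cell specimens from those study participants will be used in the immunological assays". The note states no limit by site, hookworm exposure, Na-GST-1 dose or GLA-AF.

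Section 2.1.6 says that SVI-10-01 tested Na-GST-1 "in both hookworm-unexposed (n=36) and hookworm-exposed (n=66) healthy adults". The first part was run "in Belo Horizonte, a large urban area in the Brazilian state of Minas Gerais, in healthy, hookworm-unexposed adults (n=36"). The second part was in Americaninhas: 60 participants received up to 100 µg Na-GST-1/Alhydrogel with or without 2.5 µg GLA-AF, "or the recombinant hepatitis B vaccine (n=6"). Participants "are being followed for 12 months after the final vaccination". Section 2.2.2 gives the Na-GST-1 doses in SVI-10-01 as 10, 30 and 100 µg.

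In the present trial (Sections 4 and 5.3.2) all 60 subjects live in the Americaninhas area and all receive Na-APR-1 (M74). Thirty of them (5 in each of 6 groups) also receive 100 µg Na-GST-1, with no GLA-AF in that injection. Under the secondary objective in Section 11.4, item d is a regression with Na-GST-1 at 0 or 100 µg and GLA-AF at 0 or 5 µg.

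**The concern.** No one in this trial receives Na-GST-1 without Na-APR-1 (M74). Yet every hypothesis in Section 11.1 compares co-administration with either product alone, and the secondary objective covers antibody to each antigen. The Na-GST-1 half of those questions therefore rests on SVI-10-01. Section 2.2.3 adds that the doses and components of a co-formulated product will be chosen from the cumulative results of this trial and the earlier Phase 1 trials.

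The protocol itself gives a reason not to treat exposed and unexposed adults as interchangeable. Section 2.1.3 reports that a different hookworm antigen was well tolerated in hookworm-naïve adults and then caused generalised urticaria in previously infected adults in Americaninhas.

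The misdescription also has a practical effect. Someone drafting the detailed analysis plan who trusts the Section 11.4 sentence would see no need to select a subset. If a subset is then chosen after the SVI-10-01 results are known, the comparator is open to choice. Section 2.2.2 already cites some of those results.

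**Working it through.** **1. Reproduce the protocol's count.** Section 2.1.6 gives 36 unexposed + 66 exposed = 102, and in Americaninhas 60 + 6 = 66. Both agree with the total of 102 in Section 2.2.2.

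**2. Set each part of SVI-10-01 against the present trial.**

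| SVI-10-01 participants | n | Share of 102 | Same site and population? | Received Na-GST-1? |
|---|---|---|---|---|
| Belo Horizonte, unexposed | 36 | 35.3% | No | Yes |
| Americaninhas, hepatitis B vaccine | 6 | 5.9% | Yes | No |
| Americaninhas, Na-GST-1 | 60 | 58.8% | Yes | Yes, up to 100 µg, with or without 2.5 µg GLA-AF |

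Only the first row contradicts the Section 11.4 sentence. Among Na-GST-1 recipients the unexposed share is 36/(36 + 60) = 36/96 = 37.5%.

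**3. Size of a possible bias.** Suppose the comparator were formed from all 96 Na-GST-1 recipients. Let Δ be the mean log IgG in unexposed minus exposed recipients. The comparator mean then shifts from the exposed mean by 0.375 × Δ. The documents give neither the size nor the sign of Δ, so the shift could hide interference or create an appearance of it.

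**4. Fit to the trial's own model.** Item d has no level for 10 or 30 µg Na-GST-1 and none for 2.5 µg GLA-AF. It also lists Na-APR-1 only at 10, 30 and 100 µg, so it does not say how a subject without Na-APR-1 enters. The level list points towards a 100 µg comparator but does not state one.

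**5. What restriction does to precision.** The documents do not give the number in Americaninhas who received 100 µg without GLA-AF. As an assumption only, an even spread of the 60 over 3 doses × 2 formulations gives 60/6 = 10. The values 6 and 20 below are illustrative bounds, not documented figures. The columns are:

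- the chance of seeing at least one event with a true rate of 5%, 1 − 0.95ⁿ;
- the upper two-sided 95% limit with zero events, 1 − 0.025^(1/n);
- the standard-error factor for a difference in mean log IgG against 30 co-administered subjects, √(1/30 + 1/n), assuming a common SD.

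| n | ≥1 event at 5% | Upper limit, 0 events | SE factor |
|---|---|---|---|
| 6 | 26.5% | 45.9% | 0.447 |
| 10 | 40.1% | 30.8% | 0.365 |
| 20 | 64.2% | 16.8% | 0.289 |
| 60 | 95.4% | 6.0% | 0.224 |
| 96 | 99.3% | 3.8% | 0.209 |

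The first formula reproduces the Section 11.2 table (64.15% at n = 20 and 95.39% at n = 60 for a 5% event).

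**6. A related discrepancy.** Section 2.2.2 describes Na-GST-1 as "administered to 102 healthy Brazilian adults (protocol SVI-10-01"), whereas Section 2.1.6 implies 36 + 60 = 96 recipients. The two should be reconciled.

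**The case against.** Several stronger readings are tempting, and the documents do not support them.

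- **That 42 of 102 contradict the sentence.** A reader might add the 6 hepatitis B recipients to the 36. They were in Americaninhas, so site and population match. They are unsuitable because they had no Na-GST-1, and Section 11.4 already speaks of specimen data on recipients of Na-GST-1/Alhydrogel.
- **That the plan pools all Na-GST-1 doses.** It does not say so. Item d uses 0 and 100 µg, and the adverse event summaries in Section 11.4 are by dose. What stands is that no restriction is stated either.
- **That safety counts cannot be compared because follow-up differs (12 v 9 months).** The outcome windows in Section 11.4 run to about 9 months, and longer historical follow-up can be cut to them. Section 9.1 gives 12 months for serious events, but that is a separate inconsistency.
- **That GLA-AF recipients would distort the reference.** Section 2.2.2 reports no significant IgG gain from GLA-AF with Na-GST-1, and Section 2.3.1 reports similar reactogenicity. Non-significance is not equivalence, but the protocol's evidence makes this the weaker concern. Also, 15 of the 30 co-administered subjects (Groups 2, 4 and 6) receive 5 µg GLA-AF in the other arm, so a comparator strictly without GLA-AF is not an exact match for systemic reactions.

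It can also be said that choosing a historical subset is ordinary work for the detailed plan that Section 11.4 promises, and that the sentence itself points to the correct account in Section 2.1.6. That would answer a complaint about missing detail. It does not answer a sentence that is wrong and on which the comparison relies.

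Finally, Section 2.1.4 argues that natural infection does not raise IgE to Na-GST-1, and Section 2.1.6 reports good tolerability in both populations. The effect on safety may therefore be small. Neither statement settles antibody levels.

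**Conclusion.** The point holds. Section 11.4 misdescribes its comparator: 36 of 102 participants (35%), or 36 of 96 Na-GST-1 recipients (37.5%), were neither at this site nor from this population. The other 60 recipients include doses and an adjuvant level that the trial's own regression cannot accommodate. Used as described, the comparator could bias the only Na-GST-1-alone comparison.

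The counts come straight from the protocol. The size and direction of any bias do not. They depend on differences by exposure and dose that the documents do not report, and on how the comparator is actually assembled. If IgG rises with Na-GST-1 dose (an assumption), including lower-dose recipients would lower the reference and could mask interference.

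Severity is moderate. A reader might infer that the trial's main results are compromised. They are not: the randomised comparison of Na-APR-1 (M74) with and without Na-GST-1 carries the primary objective and the anti-Na-APR-1 half of the secondary objective, and it does not use SVI-10-01. The study is also declared descriptive and not powered for group differences (Sections 11.1 and 11.2).

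**What to change.** In Section 11.4:

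- Correct the sentence so that it says only the Americaninhas part of SVI-10-01 shares this trial's site and population.
- Restrict the main historical comparator to Americaninhas participants who received 100 µg Na-GST-1/Alhydrogel without GLA-AF. Show the GLA-AF recipients separately as a sensitivity display.
- Apply the outcome windows listed in Section 11.4 to the historical safety data.
- Label every comparison with SVI-10-01 as non-randomised, and say in which model the historical subjects enter.
- Report the number of participants in the restricted comparator, and reconcile the count of Na-GST-1 recipients between Sections 2.1.6 and 2.2.2.

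The change is to wording in the protocol and analysis plan, with no new subjects or visits. The cost is a smaller comparator, of a size the documents do not give, and hence wider intervals. If it were about 10 (an assumption), the standard-error factor against the 30 co-administered subjects would be 0.365, compared with 0.209 if all 96 recipients were used.
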